8.3.2. End of Study

At End of Study (EOS) for each subject, disposition will be recorded. EOS will occur at the earliest of the following:

- Long-term follow-up is complete
- Voluntary withdrawal by the subject from the study
- Subject death
- Closure of the study by the Sponsor

Completion of the conduct of the study is defined as the date of the last visit of the last subject.

8.4. Study Termination

The Sponsor has the right to terminate the study at any time if judged necessary for safety, regulatory, or other reasons consistent with applicable laws, regulations, and Good Clinical Practice (GCP). In this event, the Investigator(s) will be informed of the reason for study termination. Should this occur, all data available will also be recorded in the eCRFs. The Investigator should notify the relevant Institutional Review Boards (IRBs)/Independent Ethics Committees (IECs) in writing of the study's completion or early discontinuation.

9. ADVERSE EVENTS AND SERIOUS ADVERSE EVENTS

9.1. Adverse Event Reporting

9.1.1. Definitions

An AE is defined as any untoward medical occurrence in a clinical study subject administered a medicinal product, which does not necessarily have a causal relationship with this treatment. An AE can therefore be any unfavorable and unintended sign (including an abnormal laboratory finding), symptom, disease, or medical condition temporally associated with the use of a medicinal (investigational) product, whether or not it is related to the medicinal (investigational) product. This includes an exacerbation of pre-existing conditions or events, intercurrent illnesses, or drug interaction. Anticipated fluctuations of pre-existing conditions, including the disease under study, that do not represent a clinically significant exacerbation or worsening need not be considered AEs.

Progression of the underlying malignancy that is clearly consistent with the progression as defined by RECIST v1.1 criteria (or PCWG3 criteria in the setting of mCRPC), or other protocol defined criteria, is not considered an AE. Hospitalization due solely to progression of the underlying malignancy should not be reported as an SAE.

If signs, symptoms and/or physical findings cannot be determined as exclusively due to progression of the underlying malignancy or do not fit the expected pattern of progression, these clinical symptoms should be reported as AEs or SAEs.

If there is any uncertainty regarding an AE or SAE being due to progression of malignancy, these should be reported as AEs or SAEs.

Signs and symptoms associated with overdose of KZR-261 must be reported as AEs.

It is the responsibility of the Investigator to document all AEs that occur during the study. AEs will be elicited by asking the subject a nonleading question, for example, "Have you experienced any new or changed symptoms since we last asked/since your last visit?" AEs should be reported on the appropriate page of the eCRF.

9.1.2. Assessment of Severity

Severity of AEs will be graded according to NCI CTCAE v5.0. If there is a change in severity of an AE, it must be recorded as a separate event. For AEs not listed in the NCI CTCAE, the Investigator should determine the severity of the AE according to the criteria in [Table 11](#).

Table 11: Adverse Event Severity Assessment

Grade 1 (Mild)	Mild; asymptomatic or mild symptoms; clinical or diagnostic observations only; intervention not indicated.
Grade 2 (Moderate)	Moderate; minimal, local or noninvasive intervention indicated; limiting age-appropriate instrumental activities of daily living.
Grade 3 (Severe)	Severe or medically significant but not immediately life-threatening; hospitalization or prolongation of hospitalization indicated; disabling; limiting self-care activities of daily living.
Grade 4 (Life-threatening)	Life-threatening consequences; urgent intervention indicated.
Grade 5 (Death)	Death related to the adverse event.

9.1.3. Assessment of Causality

The Investigator will assess the causal relationship between study drug and an AE. AEs will be deemed related to study drug unless irrefutably determined to be related to the disease under study or another non-study drug cause.

The causal relationship between the study drug and the AE will be assessed using 1 of the following 2 categories:

Unrelated: An AE is not associated with study drug if any of the following is true:

- A temporal relationship is lacking (ie, the event did not occur within a reasonable time frame after administration of the study drug)
- Other causative factors more likely explain the event (eg, intercurrent illness, concomitant treatments, traumatic event).
- The AE did not reoccur upon re-administration of the study drug (if applicable)

Related: An AE is attributed to the study drug if any of the following is true:

- There is a positive temporal relationship (ie, the event occurred within a reasonable time frame after administration of study drug)
- The AE is more likely explained by the study drug than by another cause and cannot be clearly assessed as “unrelated”

Reporting of unexpected adverse reactions is described in [Section 9.5](#).

9.1.4. Action Taken

The Investigator will describe the action taken with study drug in the appropriate section of the eCRF, as follows:

- None
- Study drug stopped
- Study drug temporarily interrupted
- Study dose modification
- Other, specify

9.1.5. Follow-up of Adverse Events

AEs are intended to be collected according to the procedures outlined above from the time of ICF and are to continue for 30 days following the last dose of study drug.

All Investigators should follow up with subjects with AEs until the event is resolved or until, in the opinion of the Investigator, the event is stabilized or determined to be chronic. Details of AE resolution must be documented in the eCRF.

9.1.6. Documentation and Reporting of Adverse Events

AEs (including SAEs) should be reported and documented in accordance with the procedures outlined below. All AEs occurring during the study must be documented on the relevant eCRF pages. The following data should be documented for each AE:

- Diagnosis or description of the symptom if diagnosis is not established
- Classification of ‘serious’ or ‘not serious’
- Severity
- Date of first occurrence and date of resolution (if applicable)
- Action taken with study drug
- Causal relationship with study drug
- Whether medication or therapy was given
- Outcome of event (unknown, recovered, not yet recovered, recovered with sequelae, death [with date and cause reported])

9.2. Serious Adverse Events

9.2.1. Serious Adverse Events Definition

An SAE is any untoward medical occurrence or affect that, at any dose:

- Results in death
- Is life-threatening (an AE is life-threatening if the subject was at immediate risk of death from the event as it occurred, ie, it does not include a reaction that might have caused death if it had occurred in a more serious form)
- Requires or prolongs inpatient hospitalization. (Complications occurring during hospitalization are AEs and are SAEs if they cause prolongation of the current hospitalization. Hospitalization for elective treatment of a pre-existing non-worsening condition is not, however, considered an AE. The details of such hospitalizations must be recorded on the medical history or physical examination page of the eCRF)
- Results in persistent or significant disability/incapacity. (An AE is incapacitating or disabling if it results in a substantial and/or permanent disruption of the subject’s ability to carry out normal life functions)

- Results in a congenital anomaly/birth defect
- Is an important medical event that requires medical and scientific judgement to decide if prompt notification is required in situations other than those defined for SAEs above. This may include any event that the Investigator regards as serious that did not strictly meet the criteria above but may have jeopardized the subject and may require medical or surgical intervention to prevent one of the other outcomes listed above.

9.2.2. Serious Adverse Event Reporting and Documentation Requirements

Any SAE must be reported as detailed in [Section 9.1.6](#) by the Investigator if it occurs from the time of signed consent through 30 days after the last dose of study drug, whether or not the SAE is considered to be related to the investigational product. All Investigators should follow up with subjects with SAEs until the event is resolved or until, in the opinion of the Investigator, the event is stabilized or determined to be chronic. Details of SAE resolution must be documented.

An SAE report consists of the SAE form, provided separately. If considered necessary, additional redacted source documents regarding an SAE may be requested.

Redacted source documents (ie, medical records) should not be provided in lieu of a completed SAE report form.

SAEs that occur during the reporting period must be reported by the Investigator to the [REDACTED] Safety Reporting e-mail address [REDACTED], or dedicated fax [REDACTED] (see also Study Personnel page at the front of this protocol) and entered into electronic data capture (EDC) within 24 hours from the point in time when the Investigator becomes aware of the SAE.

The Investigator should not wait to receive additional information to fully document the event before notification of a SAE, though additional information may be requested. Where applicable, information from relevant laboratory results, hospital case records, and autopsy reports should be obtained.

Instances of death, congenital abnormality, or an event that is of such clinical concern as to influence the overall assessment of safety, if brought to the attention of the Investigator at any time after cessation of study drug administration and considered by the Investigator to be related to participation in this study, should be reported to the study monitor.

The Sponsor and/or the Contract Research Organization (CRO) will promptly notify all relevant Investigators and the regulatory authorities of findings that could adversely affect the safety of subjects, impact the conduct of the study or alter the IEC/IRB approval/favorable opinion of the study. In addition, the CRO and the Sponsor will expedite the reporting to all concerned Investigators, to the IECs/IRBs, where required, and to the regulatory authorities of all adverse reactions that are both serious and unexpected ([Section 9.5.1](#)).

9.3. Pregnancy Reporting

Pregnancy occurring in a subject or partner of a subject during a clinical investigation must be reported within 24 hours on a Pregnancy Monitoring Form. The outcome of a pregnancy should be followed up carefully and any abnormal outcome of the mother or the child should be reported. This also applies to pregnancies following the administration of the investigational

product to the father prior to sexual intercourse. Infants should be followed for a minimum of 8 weeks, and all findings should be reported to the Sponsor. Study drug is to be discontinued immediately upon Investigator knowledge of pregnancy in a subject.

If the outcome of the pregnancy meets a criterion for immediate classification as an SAE-spontaneous abortion (any congenital anomaly detected in an aborted fetus is to be documented), stillbirth, neonatal death, or congenital anomaly—the Investigator should repeat the procedures for expedited reporting of SAEs ([Section 9.2.2](#)).

Full details will be recorded on the withdrawal page of the eCRF, or an SAE report will be completed if the subject has completed the study.

9.4. Adverse Events of Special Interest

There are no identified AEs of special interest for this FIH study that require expedited reporting.

9.5. Unexpected Adverse Reactions

9.5.1. Unexpected Adverse Reaction Definition

An unexpected adverse reaction is any untoward or unintended response that is related to the administration of the study drug at any dose that is not consistent with the applicable product information (eg, not listed in the Reference Safety Information section of the Investigator's Brochure or prescribing information or not listed at the specificity or severity it has been observed).

All suspected unexpected serious adverse reactions (SUSARs) will be subject to expedited reporting. The Sponsor and/or the CRO shall ensure that all relevant information about a SUSAR that is fatal or life-threatening is reported to the relevant competent authorities and IEC/IRB within 7 days after knowledge by the Sponsor of such a case and that relevant follow-up information is communicated within an additional 8 days. All other SUSARs will be reported to the relevant competent authorities and IEC/IRB within 15 days after knowledge by the Sponsor of such a case. Also, all Investigators that are involved in the current study and any study with KZR-261 will be informed regarding a SUSAR occurrence.

All Investigators should follow up SUSARs until the event is resolved or until, in the opinion of the Investigator, the event is stabilized or determined to be chronic. Post-study SUSARs that occur after the subject has completed the clinical study must be reported by the Investigator to the Sponsor in the same manner.

10. STATISTICAL ANALYSES

A detailed Statistical Analysis Plan will be prepared by the Sponsor and finalized prior to database lock.

10.1. Sample Size Estimates

10.1.1. Part 1

The sample size for Part 1 will be approximately 70 subjects, but the actual sample size will depend on the number of dose levels of KZR-261, number of subjects per dose level, and the number of subjects treated at the MTD or the MAD(s) of KZR-261.

Dose escalation will continue accruing until one of the three stopping conditions below is triggered:

- The maximum sample size has been achieved,
- MTD/MAD has been identified with sufficient accuracy: data from 6 to approximately 12 subjects have been accumulated at a dose that is deemed to be the MTD/MAD, or
- All doses explored appear to be overly toxic and the MTD cannot be determined.

Due to binomial data variability in small samples, DLTs may be observed in a first cohort(s) by chance even when the true probability (DLT) is fairly low. This could result in the estimated posterior DLT rate exceeding the targeted 30% very early in the trial, triggering an early stop when very few subjects (2-4) have been treated. To prevent stopping the trial prematurely in such cases, a step-down option with a lower dose of 0.9 mg/m^2 is added to the dose grid. This dose will be explored only if a high DLT rate occurs in the first cohort assigned to 1.8 mg/m^2 , ie, it will not be used as a starting dose and the algorithm will always assign the first cohort of subjects to a dose of 1.8 mg/m^2 .

10.1.2. Part 2A

The sample size in Part 2A is based on clinical and statistical considerations. Upon identification of the MTD/MAD at the conclusion of Part 1, the study will continue with up to 4 tumor-specific expansion cohorts and 1 All-Tumors cohort in Part 2A. The tumor-specific cohorts ($n = 15$ at interim) may be increased up to 35 subjects per cohort to more precisely estimate the anti-tumor activity of KZR-261, if there is a sufficient efficacy signal at the interim analyses (Section 10.6) and if the tumor type is not selected for investigation in Part 2B (dose optimization). The All-Tumors cohort may enroll up to 35 biopsy-evaluable subjects.

10.1.3. Part 2B

In Part 2B (Dose Optimization), up to 120 subjects (30 per each tumor-specific cohort [15 per dose level]) may be enrolled into up to 4 tumor-specific cohorts based on the totality of data after the MTD/MAD has been determined. The sample size for Part 2B is based on clinical considerations.

10.2. Analysis Populations

Three (3) analysis populations are planned for the study as follows:

- The Safety Population consists of all subjects who receive at least 1 dose of study treatment (KZR-261) and will be used for the safety analyses.
- The Response Evaluable Population is defined as all subjects who receive at least 1 dose of study treatment (KZR-261) and who have a baseline and at least 1 post-baseline anti-tumor response assessment using RECIST v1.1.
- The PK Analysis Population consists of all subjects who receive at least 1 dose of KZR-261 and who have at least one post-dose PK sample with measurable concentration of KZR-261. Any protocol deviations affecting PK analyses may result in exclusion from summaries for individual time point concentrations, complete profiles, and/or PK parameters. These exclusions will be reviewed before database lock and confirmed with the Sponsor before implementation.

Unless otherwise specified, all data will be summarized by dose level and overall for Part 1 (Dose Escalation), tumor-specific cohort for Part 2A (Dose Expansion), and dose and tumor-specific cohort for Part 2B (Dose Optimization).

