2.1.2. Primary Objective for Parts 2A and 2B (Dose Expansion and Dose Optimization)

- To further characterize the safety profile of KZR-261 and identify the recommended Phase 2 dose (RP2D).

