3. STUDY DESIGN

3.1. Overview of Study Design

This FIH, open-label, multicenter, Phase 1 study is designed to assess the safety and tolerability, preliminary anti-tumor activity, and the PK characteristics of KZR-261, as well as identify the RP2D. KZR-261 will be administered as a 30- to 60-minute IV infusion via a central line on Days 1, 8, and 15 of a 4-week (28-day) treatment cycle. (Doses may be held up to 7 days for resolution of non-DLT toxicity.) Eligible subjects will have locally advanced or metastatic solid malignancies and no approved therapies, or refused such therapies if available.

The study will be conducted in 2 parts: Part 1 (Dose Escalation) and Part 2 (Part 2A –Dose Expansion and Part 2B – Dose Optimization).

[figure not shown]
In Part 1, increasing doses of KZR-261 will be administered in an “i3+3” design to approximately 70 subjects to evaluate the safety and tolerability, PK, and pharmacodynamics of KZR-261, including identifying the MTD or MAD.

The Dose Expansion phase will commence following determination of the MTD/MAD and a review of the totality of safety data from Part 1. Part 2A will further characterize the safety profile of KZR-261 at the MTD or MAD and evaluate the anti-tumor activity of KZR-261 in subjects who have select malignancies. Up to 175 subjects may be enrolled in up to 4 tumor-specific cohorts (such as malignant melanoma [including uveal melanoma], mesothelioma, mCRPC, and mCRC) and 1 “All-Tumors” cohort. Additional or different tumor-specific cohorts may be investigated at the Sponsor’s discretion. Each tumor-specific cohort will enroll 15 subjects during Stage 1, expanding up to 35 subjects (Stage 2) as defined by a prespecified futility analysis and if the tumor type is not selected for investigation in Part 2B (see below). If futility is not rejected after Stage 1 (ie, prespecified criteria for futility are met), subsequent enrollment to that Part 2A cohort will cease. The All-Tumors cohort may enroll up to 35 biopsy-evaluable subjects.

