#### Definition of MTD, MAD, and RP2D

The estimated MTD is the dose level associated with approximately 30% of DLT-evaluable subjects experiencing a DLT. The target interval for the DLT rate is 25%-35%. Due to the discreteness of the dose levels and in the interest of the safety of subjects, the estimated MTD is the highest tested dose level with DLT rate  $\leq 35\%$  in at least 6-12 DLT-evaluable subjects. In general, the MTD will equal the RP2D unless one or more of the following suggest that an alternate dose below the MTD would be preferable:

- Clinically significant anti-tumor effect.
- The MTD is not achieved, in which case the MAD may become the RP2D.
- The occurrence of late and relevant AEs that occur after the DLT period.
- Cumulative toxicity of the MTD or MAD, reflecting that the administration of multiple cycles at the MTD or MAD is not feasible.
- AEs observed beyond Cycle 1 that would require setting the RP2D below the MTD level.

The SRC will evaluate the totality of the events and consider whether they could result from a cumulative toxicity or are significant for the determination of the RP2D.

The MAD is declared without an MTD based on a dose level with an observed DLT rate <25% (the lower bound of the MTD range) and where sufficient safety and efficacy signals have been observed.

The RP2D is the dose chosen for further study based on Phase 1 study results. The RP2D will take into account late and relevant toxicities that occur after the DLT period and/or the cumulative tolerance of multiple cycles of treatment. If the MTD or MAD proves to be clinically feasible for long-term administration in a reasonable number of subjects, then this dose usually becomes the RP2D. Further experience with the MTD/MAD may result in a RP2D dose lower than the MTD/MAD (eg, if in the expansion part >25% of subjects require a dose reduction due to toxicity, then the sponsor may convene an SRC to determine if a lower RP2D needs to be determined).

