An overall summary that includes the number and percentage of subjects who experienced at least one TEAE, including treatment-related TEAEs, SAEs, treatment-related SAEs, TEAEs leading to treatment interruption, dose reduction, discontinuation, death, and Grade 3 or 4 TEAEs will be provided. TEAEs will be summarized by dose level in Part 1 (Dose Escalation) and by tumor cohort in Parts 2A and 2B (Tumor-Specific Dose Expansion and Dose Optimization) All verbatim TEAEs will be coded to a MedDRA system organ class (SOC) and preferred term (PT). If a subject reports the same PT multiple times within a SOC, that PT will be counted once (at the highest level of severity) within that SOC. If a subject reports multiple different PTs within the same SOC, a subject will be counted once at the SOC level. SOCs and PTs will be listed in order of descending frequency within each SOC.

Summaries of TEAEs by maximal severity will be presented.

All AEs will be presented in a subject listing.

The following will be presented as listings and summary tables:

- TEAEs leading to study treatment discontinuation
- TEAEs related to KZR-261
- TESAEs
- TESAEs related to KZR-261
- TEAEs related to KZR-261 leading to early treatment discontinuation
- TEAEs leading to dose reduction
- TEAEs leading to death by category (Death on-treatment, Death post-treatment, and all death)
- TEAEs related to KZR-261 leading to death
- Grade 3 or 4 TEAEs
- Grade 3 or 4 TEAEs related to KZR-261
- Selected TEAEs by category (such as neutropenia and neutrophil count decreased, QTc prolongation and cardiac toxicities, liver toxicity, nephrotoxicity, bone marrow toxicity, etc)

In addition, all SAEs will be presented in a separate listing.

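### Part 2A is meant to describe safety at the MTD/MAD, but its adverse events and dose reductions are tabulated only by tumor cohort, with no planned pooled rate by assigned dose

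*Protocol*

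**What the plan says.** Protocol 2.1.2 gives the primary objective for Parts 2A and 2B: "To further characterize the safety profile of KZR-261 and identify the recommended Phase 2 dose (RP2D". Protocol 3.1 gives the purpose of Part 2A: "Part 2A will further characterize the safety profile of KZR-261 at the MTD or MAD". On size, the same section says "Up to 175 subjects may be enrolled in up to 4 tumor-specific cohorts", with an All-Tumors cohort in addition. Tumor-specific cohorts start at 15 subjects and, under Protocol 10.1.2, "may be increased up to 35 subjects per cohort to more precisely estimate the anti-tumor activity". For the fifth cohort, "The All-Tumors cohort may enroll up to 35 biopsy-evaluable subjects".

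On grouping, Protocol 10.2 sets the default: "all data will be summarized by dose level and overall for Part 1 (Dose Escalation), tumor-specific cohort for Part 2A (Dose Expansion". SAP 7.4 repeats it. In both places the overall column belongs to Part 1, and Part 2B is grouped by dose and tumor cohort. SAP 15.1 then says of adverse events: "TEAEs will be summarized by dose level in Part 1 (Dose Escalation) and by tumor cohort in Parts 2A and 2B". SAP 11.2 summarizes dose reductions for the Safety Population without naming a grouping, so the SAP 7.4 default applies.

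On use of the results, SAP 4.1.1 describes when the RP2D might be set below the MTD/MAD and gives an example: "if in the expansion part >25% of subjects require a dose reduction due to toxicity". In that case the sponsor may convene the SRC.

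**The concern.** The grouping does not match the objective. Part 2A asks how tolerable one dose is across all subjects who receive it. The adverse-event tables answer a different question, namely what happened in each tumor cohort. Part 1 does get an overall column, although its dose levels in SAP Table 2 run from 1.8 to 80 mg/m² and a total across them describes no single dose.

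The SAP's own example needs a rate for the whole expansion part. Its two possible sources are the table of TEAEs leading to dose reduction (SAP 15.1) and the exposure summary (SAP 11.2), and both are split by cohort. At stake is the precision and clarity of the main safety estimate behind the RP2D: a reader of the planned output gets up to five imprecise rates and must build the relevant one.

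A second mismatch affects Part 2B. The default groups it by dose and tumor cohort, but SAP 15.1 says tumor cohort only. Read literally, SAP 15.1 merges the two randomized doses in the adverse-event tables that should separate them.

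**Working it through.** **1. Enrollment.** Inputs are from Protocol 3.1 and 10.1.2: four tumor-specific cohorts of 15, up to 35 each, and an All-Tumors cohort of up to 35.
- Ceiling: 4 × 35 + 35 = 175, which reproduces the stated maximum.
- All four tumor cohorts stop at 15 and All-Tumors reaches 35: 4 × 15 + 35 = 95.

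**2. Planned groupings for Part 2A.**

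| Data | Place | Grouping | Overall or all-treated summary? |
|---|---|---|---|
| Default | Protocol 10.2, SAP 7.4 | tumor cohort | no (Part 1 only) |
| TEAEs, including those leading to dose reduction | SAP 15.1 | tumor cohort | no |
| Exposure and dose reductions | SAP 11.2 | default applies | no |
| Laboratory, vital signs, ECG | Protocol 10.5.4 | dose or treatment group | yes |
| Vital signs, laboratory | SAP 15.3, 15.5 | tumor cohort | all actively treated subjects mentioned |

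The overview of TEAEs in SAP 15.1 covers many event categories, but the sentence that follows it sets the grouping by tumor cohort. It is not a pooled column.

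**3. Precision of an event rate near 15%.** The 15% is an illustrative assumption; the documents give no expected rate. The measure is the exact (Clopper-Pearson) 95% interval for x events in n subjects: lower limit = 0.025 quantile of Beta(x, n − x + 1), upper limit = 0.975 quantile of Beta(x + 1, n − x).

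| Column | x/n | Rate | 95% interval | Width (points) |
|---|---|---|---|---|
| One full cohort | 5/35 | 14.3% | 4.8–30.3% | 25.5 |
| Pooled, n = 95 | 14/95 | 14.7% | 8.3–23.5% | 15.2 |
| Pooled, ceiling | 26/175 | 14.9% | 9.9–21.0% | 11.1 |

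The pooled interval is 15.2/25.5 = 60% as wide as that of a full single cohort at n = 95, and 11.1/25.5 = 44% as wide at n = 175.

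**4. Precision at the SAP's 25% figure.** The smallest counts above 25% are 4/15, 9/35, 24/95 and 44/175. Their exact 95% intervals are:
- 4/15: 7.8–55.1%
- 9/35: 12.5–43.3%
- 24/95: 16.9–35.2%
- 44/175: 18.9–32.2%

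A cohort rate just above 25% says little about whether the rate for the expansion part is above 25%.

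**The case against.** The case on the other side is substantial, and much of it stands.

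- **The pooled rate can be recovered.** The cohorts do not overlap, so numerators and denominators can be added. TEAEs leading to dose reduction are both tabulated and listed, and SAP 1 allows supplementary analyses. A reader might infer that safety at the Part 2A dose is never estimated. The documents do not support that. Laboratory, vital-sign and ECG changes are also primary safety endpoints, and they have an overall or all-treated summary (ECG in Protocol 10.5.4 only).
- **The 25% figure is an example and is permissive.** The SRC would consider it during the study, from its periodic safety review, whereas SAP 7.4 places the planned tables after database lock. Their layout does not limit what the SRC sees. A reader might also infer that the figure has no counterpart in the tables. In fact reductions are counted by cohort, and only the pooled figure is absent.
- **No passage applies 25% cohort by cohort.** A reader might calculate how often at least one cohort crosses it by chance. At an assumed true rate of 15%, P(at least 4/15) = 0.177 and P(at least 9/35) = 0.069. Four cohorts of 15 and one of 35 then give 1 − (1 − 0.177)⁴ × (1 − 0.069) = 57%, against 0.6% for the pooled 95. This shows why cohort rates should not stand in for the pooled one. It is not a false-alarm rate of the plan, whose wording is already pooled.
- **A single dose is not guaranteed.** SAP 4.1.2 and 4.2.2 allow an SRC recommended dose in place of the MTD/MAD. This is a reason to pool by assigned dose, not a reason against pooling.

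What remains is that an SAP fixes what will be reported, and the summary that best matches the Part 2A objective is not among the planned adverse-event or exposure tables. The plan already accepts combining subjects on the same dose across parts: Protocol 10.6 lets Part 1 outcomes at the Part 2A dose count toward the interim efficacy look.

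**Conclusion.** The point holds as a gap in planned reporting. No adverse-event or exposure table gives the pooled Part 2A rate by assigned dose, although the primary aim of that part is safety at the MTD/MAD and SAP 4.1.1 words its 25% example for the expansion part as a whole. Data are not lost and the primary safety result is not unobtainable.

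The size is the gain in precision shown above: for an event near 15%, an interval 25.5 points wide in a full cohort narrows to 15.2 points at 95 subjects and 11.1 at the ceiling of 175. This rests on an assumed 15% rate, on treating pooled subjects as one binomial sample, and on the enrollment scenarios shown. If toxicity differs by tumor type, the pooled rate is an average over the enrolled mix, so the cohort columns should stay. The plan specifies exact intervals for efficacy rates but none for adverse-event rates; the intervals here only measure precision.

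The conflict between SAP 15.1 and the Part 2B default is a separate inconsistency that needs correction in any case. The change is worth making before the tables are programmed.

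**What to change.** 1. In Protocol 10.2 and SAP 7.4, 11.2 and 15.1, keep the tumor-cohort columns and add an all-Part-2A column by assigned dose to the TEAE, dose-modification and exposure tables.
2. In the same tables, add a column for all subjects who started at that dose in any part, including Part 1 subjects and Part 2B subjects assigned to it.
3. In SAP 4.1.1, state that the 25% dose-reduction figure uses the pooled Part 2A numerator and denominator, and define both.
4. Reconcile SAP 15.1 with the Part 2B default of dose and tumor cohort, so that adverse events are shown separately for the two randomized doses.

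If only the SAP is changed, record this in SAP 19, which now reports no departures from the protocol. The cost is two extra columns and a few sentences of text. No new data or subjects are needed.
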